4.1. Overall study design

This is a Phase II/III, multicenter, multi-country, trial to assess the efficacy, safety, tolerance, and pharmacokinetics of sofosbuvir plus ravidasvir (SOF-RDV) for the treatment of HCV infection, across genotypes 1,2,3,6, among non-cirrhotic and cirrhotic with CTP class A⁵², interferon/ribavirin naïve or experienced, HCV mono-infected and HCV/HIV co-infected subjects.

The treatment duration will be 12 weeks for subjects with no cirrhosis (Metavir F0 to F3) and 24 weeks for subjects with compensated cirrhosis (Metavir F4, CTP class A).

It will also study the pharmacokinetics of RDV and, in HCV/HIV co-infected subjects, possible drugdrug interactions with antiretrovirals.

The study is performed in two stages:

- Stage 1 with a target of 300 subjects enrolled. Stage 1 will provide preliminary evidence of the efficacy, safety, tolerance and pharmacokinetics of SOF-RDV in all subgroups.

A separate stratum of the stage 1 will be defined aiming at enrolling up to 150 additional PWID (people self-declared as being active injection drug users or with recent injection drug use or for whom active injection drug use cannot be ruled out).

- Efficacy and safety results from Stage 1 will be reviewed and approved by the independent Data and Safety Monitoring Board (DSMB) which provide the recommendation to proceed with the stage 2.
- Stage 2 with a target of 300 subjects enrolled. Stage 2 aims to supplement Stage 1 results and provide additional information on the performance of SOF-RDV in the main

genotypes found in Malaysia and Thailand. People self-declared as being active injection drug users will not be enrolled.

The overall target will be 600 enrolled subjects.

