12.2. Pharmacokinetic (PK) assessments of DAAs and Antiretroviral Drugs

12.2.1. Sparse PK samples collection in HCV/HIV coinfected patients for potential drugdrug interaction detection

The presence of concomitant Antiretroviral (ARV) medications will be coded as a binary variable (e.g. one variable per ARV drug) to estimate population PK parameters in the presence of the covariate i.e. to determine the fractional change due to the presence of the concomitant ARV drug(s).

Ravidasvir pharmacokinetics

The impact of co-administered antiretroviral drugs on ravidasvir PK parameters is investigated using a population pharmacokinetic approach (morning trough concentration and other available sparse samples). HCV mono-infected subjects (except those in the intensive PK study) and HIV/HCV co-infected patients receiving an NNRTIs (e.g. efavirenz, nevirapine) or PI (e.g. lopinavir/ritonavir or atazanavir/ritonavir) will have sparse PK sampling performed.

Antiretroviral Pharmacokinetics for HIV co-infected subjects

As part of the planned sparse PK sampling for ravidasvir, antiretroviral trough concentrations will be determined in the pre-dose sample collected at week 4. In addition, for all the subjects on ART a single plasma sample (e.g. trough or mid-dose) will also be collected at study entry prior to initiating the HCV treatment. The analysis of ARV trough concentrations will be descriptive and mean concentrations will be compared to historical ranges reported in adults and the recommended cut-off concentrations for virologic efficacy.

Potential for other drug-drug interactions

Stored blood samples may be used to assess blood levels of concomitant medications

13. Timing of assessments

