16.1.3. Sample size determination for the global study

A total sample size of 600 patients will ensure that the width of the 95% CI around the overall SVR12 rate expected to be observed will be as small as 4-5% (see Figure 3). With this sample size, the lower bound of the 95% CI will be greater than 85% if the observed overall SVR12 rate is 88% or higher.

Figure 3: Confidence intervals for expected observed SVR12 rates in 300 and 600 subjects				
Observed overall	N=300		N=600	
SVR12 rate	95% CI	Width of 95% CI	95% CI	Width of 95% CI
87%	82.7% to 90.6%	7.9%	84.0% to 89.6%	5.6%
88%	83.8% to 91.4%	7.6%	85.1% to 90.5%	5.4%
89%	84.9% to 92.3%	7.4%	86.2% to 91.4%	5.2%
90%	86.0% to 93.2%	7.2%	87.3% to 92.3%	5.0%
91%	87.2% to 94.0%	6.8%	88.4% to 93.2%	4.8%
92%	88.3% to 94.8%	6.5%	89.5% to 94.0%	4.5%
93%	89.5% to 95.6%	6.1%	90.7% to 94.9%	4.2%
94%	90.7% to 96.4%	5.7%	91.8% to 95.8%	4.0%
95%	91.9% to 97.2%	5.3%	92.9% to 96.6%	3.7%

The study population will comprise up to 50% subjects with compensated cirrhosis. Based on preliminary site assessment, HIV/HCV co-infected subjects will represent approximately 30% of the study population. It is expected that 35-40% of the subjects will be infected by HCV genotype 3, 35-40% genotype 1, 15-20% genotype 6 and 5-10% genotype 2. In addition, a substantial fraction of the subjects may not be treatment naïve, and may have been previously exposed to interferon/ribavirin.

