16.1.4. Sample size for the intensive PK substudy (Stage 1)

The sample size necessary to assess drug-drug interactions in HCV/HIV co-infected subjects will be also met. It is estimated that approximately one third of the subjects will be co-infected (see section 16.1.4).

In the intensive PK substudy (Stage 1), a total of 25 subjects will be enrolled in order to ensure adequate precision of PK parameter estimates. The precision required is a mean plasma ravidasvir AUC0-24h within $\pm 20\%$ of the true population mean (i.e. margin of error). The reported coefficient of variation (CV) of the AUC in HCV-infected adults for ravidasvir is 45.8% following multiple doses once daily. This is estimated to correspond to $\pm 2,800$ ng.hr/mL for a 200 mg daily dosing. Assuming the true mean and CV for the ravidasvir AUC0-24h are the same for Thai and Malaysian subjects as in the reported studies, the sample size calculation ensured that the 95% confidence interval of the sample mean for the AUC0-24h of ravidasvir is within $\pm 20\%$ of the true mean i.e. within $\pm 2,800$ ng.hr/mL.

Based on the reported variability at the standard dose and assuming mean AUC results are normally distributed, a sample size of 25 participants (taking into account 5-10% non-evaluable) is required. This sample size would also be sufficient to ensure the same precision for sofosbuvir and the sofosbuvir metabolite (GS31007) exposure based on the reported CV% for each drug (if also measured).

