16.2.6. Pharmacokinetics

In stage 1, the pharmacokinetics of RDV will be evaluated using an intensive PK schedule for a small proportion of the subjects enrolled in healthcare institutions to establish the PK model and by population approach (sparse sampling) for the others. Twenty-five evaluable intensive PK evaluations will provide sufficient precision in the estimates of the PK parameters to use as initial estimates in the population model.

The population PK model (stage 1 and stage 2) built using these parameters allows, with a small number of samples per subject, collected at variable times between drug intake and sampling, to reestimate the pharmacokinetic parameters of the drugs as well as their variability in the population. This approach enables to explain the observed variability with various pertinent covariates such as possible antiretroviral co-treatment and patient's characteristics (e.g., BMI, sex, etc.).

Individual pharmacokinetic parameters are derived using Bayesian estimation from the population model. Association between individual exposures (i.e. trough concentration, area under the curve) and efficacy/tolerance endpoints are then investigated. The pharmaco-statistical analysis is performed using non-linear mixed effects modelling software (e.g. Monolix v4.2 or NONMEM v7.3) to calculate the pharmacokinetic parameters of all drugs as well as the covariates associated with inter-subject variability.

Given the reported drug-drug interactions between antiretrovirals and DAAs, RDV, NNRTI or PI morning troughs or mid dose concentrations are systematically measured in HIV/HCV co-infected subjects to verify that RDV as well as antiretrovirals are within exposure targets. Given the metabolic route of elimination of RDV, it is anticipated that drug-drug interactions, if any would be minimal.

Hair analysis has proved to be a suitable method to detect chronic or acute abuse of many drugs of abuse such as opiates, cocaine, amphetamines and many others. Hair samples are collected at baseline and at end of treatment for all subjects where possible. These samples will be used to assess drug use in subjects who fail to meet the primary study endpoint (SVR12).

Data management programs and all statistical analyses except pharmacokinetic modelling will be performed using Stata version 13 or higher.

17. Data Safety Monitoring Board

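### The antiretroviral check in Section 12.2.1 compares the mean trough with a per-patient efficacy cut-off, so it can look adequate while a material share of patients lies below it

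*Protocol*

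**What the plan says.** Evaluating interactions between the study drugs and antiretrovirals is a secondary objective (Protocol Section 3.1.2). Section 12.2.1 sets out the antiretroviral side of it. On treatment, "antiretroviral trough concentrations will be determined in the pre-dose sample collected at week 4". Before treatment, "a single plasma sample (e.g. trough or mid-dose) will also be collected at study entry prior to initiating the HCV treatment". The section fixes one comparison for these data, and it is made on the group average: "mean concentrations will be compared to historical ranges reported in adults and the recommended cut-off concentrations for virologic efficacy". It also states what kind of analysis this is: "The analysis of ARV trough concentrations will be descriptive".

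Section 16.2.6 returns to the same measurements and says that they are made in co-infected subjects "to verify that RDV as well as antiretrovirals are within exposure targets".

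Neither section gives a cut-off value, a historical range, an antiretroviral CV or a decision rule. Neither names a summary that sets individual subjects against the cut-off.

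**The concern.** A recommended concentration for virologic efficacy is a limit that each patient should exceed. The protocol sets the group mean against it. In a right-skewed distribution the mean is pulled up by the high values and lies above the median, so it can exceed the cut-off when half of the patients do not. The statistic therefore does not answer the question that Section 16.2.6 asks of it.

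At stake is how the antiretroviral part of the interaction objective is reported. Subjects on cART enter with HIV RNA below 50 copies/mL (Section 5.2). The schedules in Sections 7.1 and 7.2 place HIV RNA only at screening and at follow-up week 12; closer monitoring is left to clinical judgement. The week 4 trough is thus the one scheduled on-treatment look at antiretroviral adequacy, and its named summary is weakest when exposure has fallen towards the cut-off.

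**Working it through.** **No figure to reproduce.** The protocol states no sample size, power or expected share below the cut-off for this check.

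**Inputs.**
- Statistic and comparator: mean trough against the efficacy cut-off (Section 12.2.1).
- Number of subjects: "The overall target will be 600 enrolled subjects" (Section 4.1) and "HIV/HCV co-infected subjects will represent approximately 30% of the study population" (Section 16.1.3), so 0.30 × 600 = 180. This is an upper limit for any one antiretroviral, because subjects not on cART have no trough and the others are spread over several drugs.
- Variability: an assumption. The only between-subject PK variability in the protocol concerns another drug and another parameter: "The reported coefficient of variation (CV) of the AUC in HCV-infected adults for ravidasvir is 45.8" per cent (Section 16.1.4). The CV is therefore varied from 40% to 100%, with that value as one point.
- Distribution: lognormal, an assumption.

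**Formula.** Let R be the arithmetic mean divided by the cut-off, and σ² = ln(1 + CV²). Then

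share below the cut-off = Φ[(σ²/2 − ln R)/σ].

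**Worked case, R = 1.25 (ln R = 0.2231).**
- CV 40%: σ² = 0.1484, σ = 0.3853; (0.0742 − 0.2231)/0.3853 = −0.387; share 35.0%.
- CV 60%: σ² = 0.3075, σ = 0.5545; (0.1537 − 0.2231)/0.5545 = −0.125; share 45.0%.
- CV 80%: σ² = 0.4947, σ = 0.7033; (0.2474 − 0.2231)/0.7033 = +0.034; share 51.4%.

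**Share below the cut-off over the range.**

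| CV | R = 1 | 1.25 | 1.5 | 2 | 3 |
|---|---|---|---|---|---|
| 40% | 57.6% | 35.0% | 19.5% | 5.4% | 0.4% |
| 45.8% | 58.6% | 38.5% | 23.9% | 8.5% | 1.1% |
| 60% | 60.9% | 45.0% | 32.5% | 16.5% | 4.4% |
| 80% | 63.7% | 51.4% | 41.1% | 26.3% | 11.3% |
| 100% | 66.1% | 55.9% | 47.2% | 33.9% | 18.3% |

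**Read the other way.** With exactly half of the patients below, the cut-off is the median, so R = exp(σ²/2), which exceeds 1 for any CV. With a quarter below, R = exp(σ²/2 + 0.674σ). A share of 25% to 50% below thus corresponds to R from 1.48 down to 1.10 at CV 45.8%, 2.06 to 1.28 at CV 80%, and 2.48 to 1.41 at CV 100%.

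**Sampling variation.** This was simulated with 20,000 runs per case at CVs of 45.8%, 80% and 100%. With 25% of patients truly below, the sample mean exceeds the cut-off in at least 99.99% of runs at n = 20, 60 and 180. With 50% truly below, it does so in 81% to 93% of runs at n = 20, 94% to 99.7% at n = 60, and 99.7% to 100% at n = 180. A larger sample makes the mean more stable but no more informative about individuals.

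**What a count would show.** The exact 95% CI is 18.9% to 32.0% for 45/180 (25%), 14.7% to 37.9% for 15/60 (25%), and 6.0% to 15.3% for 18/180 (10%). The group of 60 is an assumption.

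**The case against.** The strongest case against has four parts.

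1. **The analysis is descriptive.** No rule, criterion or conclusion is attached to the mean. This stands. A reader might infer that the check would pass, or that exposure would be declared adequate, but the protocol provides for no such declaration. The mismatch between the statistic and the purpose in Section 16.2.6 remains.

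2. **Other summaries may be reported.** Section 16.2.3 describes continuous variables with medians, quartiles and ranges. If these covered antiretroviral troughs, a quarter or a half of patients below the cut-off would be visible in the quartile or the median. But that section is framed around participants' characteristics, and it sets nobody against a cut-off. Section 16.2.6 can be read as verification subject by subject, and an SAP, not seen here, may add the proportion below. Either would reduce the problem, but the comparison that the protocol names would still be the mean.

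3. **The size is assumed.** This stands. A reader might infer that a quarter to a half of co-infected patients will be below the cut-off. The documents do not support that: it needs a mean fairly close to the cut-off, and Section 16.2.6 expects interactions to be minimal, if there are any.

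4. **The historical range could reveal a fall.** A reader might infer that this second comparison would miss almost any interaction too. That cannot be shown either way, because the protocol gives no ranges.

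Nor do the documents support saying that a safety risk is hidden. HIV RNA is repeated at follow-up week 12 and HIV monitoring continues as standard of care, although no on-treatment HIV RNA is scheduled.

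**Conclusion.** The point holds as a weakness in a named analysis. Section 12.2.1 fixes a comparison of the mean with a threshold that applies to individuals, and that comparison cannot verify what Section 16.2.6 says it should. Under assumed lognormal troughs, a mean at 1.25 times the cut-off leaves about 35% to 51% of patients below it at CVs of 40% to 80%. At 3 times the cut-off or more, the share is at most about 18% for CVs up to 100%. These percentages rest on the assumed CV, the assumed ratio of mean to cut-off and the lognormal form. The direction does not depend on the CV: under any lognormal, the true mean is above the cut-off even when half of the patients are below it.

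Severity is low to moderate, since this is a reporting change for a secondary objective.

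**What to change.** In Section 12.2.1, make the following the main summary for each antiretroviral:

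- the number and percentage of subjects on that drug whose week 4 pre-dose concentration is below the recommended cut-off, with an exact 95% CI;
- the geometric mean and the 5th and 95th percentiles;
- a listing of the subjects below the cut-off with their available HIV RNA results.

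Keep the arithmetic mean as a secondary description only, and carry the same wording into Section 16.2.6 and the SAP.

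The cost is slightly more tabulation. The samples and assays are those already planned. Intervals will be wide for antiretrovirals that few subjects take, and the report should say so.

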13.1. Eligibility visit

Potential participants will be recruited at participating study sites.

The eligibility visit can be performed the same day than the screening visit for patients already diagnosed as HCV chronically infected.

Informed consent for enrollment in the study will be obtained during this visit.

The assessments performed at eligibility visit are detailed in section 7 Schedule of events.

13.2. Screening visit

The eligibility visit can be performed the same day than the screening visit for patients already diagnosed as HCV chronically infected.

The assessments performed at screening visit are detailed in section 7 Schedule of events.

Screening evaluations must occur prior to the subject starting any study medications, treatments, or interventions. In addition to data being collected on subjects who will enroll into the study, demographic, clinical, and laboratory data on screening failures will be captured at site on the CRF and then entered into the study database.

13.3. Day 1 visit: Study treatment initiation

Treatment initiation will follow thorough explanation of the treatment schedule, which differ according to fibrosis staging, and of the importance of adherence to therapy as well as study visits.

Subjects will be reminded of the importance of informing the team of any concomitant treatment, and reporting of new signs and symptoms. Subjects will be asked to avoid use over the counter medications, herbal preparations as medications/drinks/soup and consult the research team as needed.

13.4. On treatment visits

After treatment initiation, on treatment visits will be schedule at week-1, week-4, week-8 and week-12 for non-cirrhotic subjects. Cirrhotic subjects will have additional on treatment visits at week 16, week 20 and week 24.

Visit at week 1 will have a window of \pm 3 days. Visits at Weeks 4, 8, 12, 16, 20 and 24 have a window of \pm 7 days.

During study visits without PK sampling subjects can take the study treatment at home. During study visits with PK sampling (Intensive or sparse), subjects will be instructed to take the study treatment at the hospital. For PK visits, subjects will be instructed to fast at least 6 hours before the visit and until 2 hours after dosing at site.

On treatment visits will focus on recording vital signs, inquiring about new signs and symptoms, adherence to therapy, concomitant medications and symptom targeted clinical examination. Study drugs will be dispensed every 4 weeks until end of therapy (12 weeks for subjects without cirrhosis, or 24 weeks for cirrhotic subjects).

The PROQOL-HCV quality of life questionnaire will be administered at the W8 treatment visit.

New or discontinued concomitant prescription and nonprescription medications taken since the last on treatment study visit will be recorded, the dose, frequency, route of administrations as well as start and stop dates will need to be documented. All study drug modifications, including initial doses, subject-initiated and/or protocol-mandated modifications, inadvertent and deliberate interruptions will be recorded on CRFs at each visit. If one of the study medication has to be stopped, the subject cannot continue with the remaining study medication. The subject will need to be advised to stop ALL study medications and return for end of treatment assessment and then post treatment followup assessment.

13.5. Follow-up visits

13.5.1. SVR4, SVR 12, SVR 24 and end of study visit

The week 4 post-treatment visit will have a window of -1 day and +7 days

The week 12 post-treatment visit (SVR 12, key endpoint) will have a window of -1 day and +28 days.

The week 24 post-treatment visit (SVR 24) will have a window of -3 days and +28 days.

This final visit will focus on assessing SVR 24 weeks after treatment discontinuation. Post-treatment study follow-up is of critical importance and is essential to preserving subject safety and the integrity of the study. Subjects who discontinue study treatment must continue to be followed for collection of outcome and/or survival follow-up data.

13.5.2. Long term follow-up visits

A series of long-term follow-up visits will be implemented retrospectively for stage 1 (only for newly consented patients with virological failure) and for stage 2.

A representative subset of the cured patients (i.e achieving SVR12) will be followed up for one year after end of treatment to assess durability of response. One additional follow-up visit will be scheduled 12 months (+/- 28 days) after the end of treatment visit

All patients with virological failure at SVR12 or SVR24 will be followed up for three years after end of treatment or until they receive another treatment for HCV, whichever comes first. Five additional follow-up visits will be scheduled at one year, 18 months, 2 years, 30 months and 3 years after the end of treatment visit. Each of these long term follow-up visits has a window of +/- 28 days.

The following assessments will be performed at each long term follow-up visit, depending on cirrhosis status and achievement of SVR12 and SVR24:

	Non-Cirrhotics	Cirrhotics
Cured patients	HCV viral load and genotyping	HCV viral load and genotyping
-	Biochemistry and Haematology blood	Biochemistry and Haematology blood
(1 year FU post	sample ¹	sample ¹
end of treatment)	Symptom directed assessment	Symptom directed assessment
ŕ	AE review ²	AE review ²
Stage 2 only		INR ³
		Fibroscan ⁴
		Ultrasound⁵
Patients with virological failures (3 years FU post end of treatment)	HCV viral load and genotyping and resistance assessment Biochemistry and Haematology blood sample ¹	HCV viral load and genotyping and resistance assessment Biochemistry and Haematology blood sample ¹
Stage 1 and stage 2	Symptom directed assessment AE review ² INR ³ Fibroscan ⁴	Symptom directed assessment AE review ² INR ³ Fibroscan ⁴ Ultrasound ⁵

¹ Biochemistry and haematology including ALT and AST and bilirubine (direct and free)

²AE monitoring as per safety section

³ INR is performed to assess the evolution of the liver condition

⁴A Fibroscan is performed to assess the evolution of fibrosis

⁵ An ultrasound is performed to assess the occurrence of HCC as part as the standard of care.

14. Samples management

14.1. Sample collection

Routine blood and urine test will be collected according to the protocol schedule and will be analyzed by the laboratory of each site. These laboratories are accredited by Competent Authorities and follow locally defined Good Laboratory practices. Sponsor monitors, during site monitoring visits will monitor laboratory results, check normal ranges, verify quality assurance processes and maintenance of the laboratory equipment. For pharmacokinetic samples and hair samples, please refer to the relevant protocol sections.

14.2. Sample Labelling

Each sample will be identified with the study number, the subject initials and their unique identification number. The date and time of sampling will be written on the label.

